APPENDIX 8: PROHIBITED MEDICATIONS

Strong and Moderate CYP3A Inhibitors and Strong CYP3A Inducers

Strong CYP3A Inhibitors
Antibiotics: clarithromycin, telithromycin, troleandomycin
Antifungals: itraconazole, ketoconazole, posaconazole, voriconazole
Antivirals: boceprevir, telaprevir
Other: cobicistat, conivaptan, elvitegravir, mibefradil, nefazodone,
Protease Inhibitors: indinavir, lopinavir, nelfinavir, ritonavir, saquinavir, tipranavir
Strong CYP3A Inducers
Avasimibe, carbamazepine, mitotane, phenobarbital, phenytoin, rifabutin, rifampin (rifampicin), St.
John's wort (hypericum perforatum)
Moderate CYP3A Inhibitors
Antibiotics: ciprofloxacin, erythromycin
Antifungals: fluconazole
Protease inhibitors: amprenavir, atazanavir, darunavir, fosamprenavir
Calcium channel blockers: diltiazem, verapamil
Tyrosine kinase inhibitors (anti-cancer): imatinib
Food products: grapefruit and juice (Citrus paradisi), Seville orange and juice (Citrus aurantium)
Herbal medications: Schisandra sphenanthera
Others: aprepitant, casopitant, cimetidine, cyclosporine, dronedarone, tofisopam

APPENDIX 9: MEDICATIONS TO BE USED WITH CAUTION

Sensitive CYP2C9 Substrates or CYP2C9 Substrates with Narrow Therapeutic Index

Celecoxib¹

Phenytoin²

Warfarin²

2. Substrates with narrow therapeutic index (NTI): Drugs whose exposure-response indicates that increases in their exposure levels by the concomitant use of potent inhibitors may lead to serious safety concerns (eg, Torsade de Pointes).

^{1.} Sensitive substrates: Drugs that exhibit an AUC ratio (AUCi/AUC) of 5-fold or more when co-administered with a known potent inhibitor.

APPENDIX 10: MEDICATIONS TO BE USED WITH CAUTION

Strong CYP2C8 Inhibitors

Gemfibrozil

APPENDIX 11: FEMALES OF CHILDBEARING POTENTIAL AND CONTRACEPTION

Contraception guidelines

The Clinical Trials Facilitation Group (CTFG) recommendations related to contraception and pregnancy testing in clinical trials include the use of highly effective forms of birth control. These methods include the following:

- Combined (estrogen and progestogen containing) hormonal contraception associated with the inhibition of ovulation
 - Oral, intravaginal, or transdermal
- Progestogen-only hormonal contraception associated with the inhibition of ovulation
 - Oral, injectable, implantable
- An intrauterine device (IUD)
- Intrauterine hormone-releasing system (IUS)
- Bilateral tubal occlusion
- Vasectomized partner
- Sexual abstinence (defined as refraining from heterosexual intercourse during the entire period of risk associated with the study treatment). Total sexual abstinence should only be used as a contraceptive method if it is in line with the patients' usual and preferred lifestyle. Periodic abstinence (eg, calendar, ovulation, symptothermal, post-ovulation methods), declaration of abstinence for the duration of exposure to study drug, and withdrawal are not acceptable methods of contraception.

Of note, barrier contraception (including male and female condoms with or without spermicide) is not considered a highly effective method of contraception and if used, this method must be used in combination with another acceptable method listed above.

Definition of childbearing potential

Childbearing potential is defined as being physiologically capable of becoming pregnant. No childbearing potential is defined as one or both of the following criteria:

- Surgically sterile (bilateral salpingectomy, bilateral oophorectomy, or hysterectomy)
- Post-menopausal, defined as
 - \geq 55 years of age with no spontaneous menses for \geq 12 months OR
 - < 55 years of age with no spontaneous menses for ≥12 months AND with a post-menopausal follicle-stimulating (FSH) concentration >30 IU/mL

# LIST OF ABBREVIATIONS AND DEFINITIONS OF TERMS

Abbreviation	Term					
AE	adverse event					
ATC	Anatomical Therapeutic Chemical					
AUC	area under the plasma concentration-time curve					
BID	twice daily					
BOR	best overall response	· · · · · · · · · · · · · · · · · · ·				
BP	blood pressure					
BRCA	breast cancer susceptibility gene					
CBR	clinical benefit rate					
CI	confidence interval					
CR	complete response					
CRF	case report form					
CTCAE	Common Terminology Criteria for Adverse Events					
DCR	disease control rate					
DLT	dose-limiting toxicity					
DOR	duration of response					
ECG	electrocardiogram					
ECOG	Eastern Cooperative Oncology Group					
GCIG	Gynecological Cancer Intergroup					
HGOC	high grade ovarian cancer					
IRC	independent review committee					
MedDRA®	Medical Dictionary for Regulatory Activities					
MTD	maximum tolerated dose					
ORR	objective response rate					
OS	overall survival					
PA	protocol amendment					
PD	progressive disease					
PFS	progression-free survival					
PK	pharmacokinetics					
PR	partial response					
PROC	platinum-resistant ovarian cancer					
PSOC	platinum-sensitive ovarian cancer					
PT	preferred term					
RECIST	Response Evaluation Criteria in Solid Tumors					
SAE	serious adverse events					
SAP	statistical analysis plan					

SD	stable disease			
SOC	ystem organ class			
TEAE	treatment-emergent adverse event			
TNBC	triple negative breast cancer			
TTR	time to response			

#### 1 INTRODUCTION

The purpose of this statistical analysis plan (SAP) is to describe the procedures and the statistical methods that will be used to analyze and report results for Protocol BGB-290-102, An Open Label, Multi-Center Phase I/II Study to Evaluate Efficacy and Safety of BGB-290 in Chinese Subjects with Advanced Ovarian Cancer, Fallopian Cancer, and Primary Peritoneal Cancer, or Advanced Triple Negative Breast Cancer.

Reference materials for this statistical plan include the protocol BGB-290-102 (version 5.0, 2018-09-21 and version 1.1, 2016-08-15). This study contains 2 phases. Since majority of patients of Phase 1 were end of study before the protocol version 2.0 released, protocol version 1.1 will be referred to for the study operation of Phase 1 portion. For the final analysis, the latest version of the protocol will be referred to for both Phase 1 and Phase 2. If the protocol or case report forms are amended or updated, then appropriate adjustments to the SAP may be made if they are related to the planned analyses.

The SAP described hereafter is an *a priori* plan. This is an open label study and the SAP will be finalized and approved before database lock. Statistical programming may occur as study data accumulate in order to have analysis programs ready at the time the study finishes.

#### 2 STUDY OVERVIEW

This is a Phase 1/2, open-label, multicenter study of pamiparib administered orally twice daily (BID) to adult Chinese patients with advanced solid tumors which have progressed despite standard therapy or for which no standard therapy exists.

The Phase 1 portion of this study is designed to evaluate the safety, tolerability and PK profile of pamiparib in Chinese patients with advanced solid tumors and to determine RP2D of pamiparib for Chinese patients. In this study, three dose levels, 20 mg, 40 mg, and 60 mg BID, were evaluated. The purpose of this study is to determine the RP2D and MTD, if any, of pamiparib in Chinese cancer patients. Dose escalation will follow a modified 3+3 dose escalation design.

In the Phase 2 portion, approximately 100 evaluable patients (80 previously treated platinum-sensitive and 20 previously treated platinum-resistant) with advanced high grade (Grade 2 or Grade 3 endometrioid epithelial cancer is acceptable too), non-mucinous, epithelial ovarian cancer (including fallopian cancer, or primary peritoneal cancer) of either known deleterious or suspected deleterious *BRCA1/2* mutations who have received at least two lines of prior therapies will be enrolled.

#### 3 STUDY OBJECTIVES

#### 3.1 PHASE 1 PORTION

# 3.1.1 Primary Objectives

• To evaluate the safety and tolerability of pamiparib in Chinese patients with advanced solid

**Version 1.1**: 02/28/2020 Page 7 of 28

tumors

• To determine the recommended Phase 2 dose of pamiparib

# 3.1.2 Secondary Objectives

- To characterize the pharmacokinetics of pamiparib in Chinese patients
- To evaluate the clinical antitumor activity of pamiparib in Chinese patients with TNBC or high-grade epithelial, non-mucinous ovarian cancer (including fallopian cancer, or primary peritoneal cancer)
- To evaluate the relationship between pamiparib PK and clinical endpoints

# 3.1.3 Exploratory Objectives

\_\_\_\_\_

3.2

# 3.2.1 Primary Objectives

PHASE 2 PORTION

• To evaluate the efficacy of pamiparib as measured by objective response rate (ORR) according to Response Evaluation Criteria in Solid Tumors (RECIST), version 1.1 (RECIST v1.1), by independent review committee (IRC) in patients with advanced platinum-sensitive or platinum-resistant high grade, non-mucinous, epithelial ovarian cancer (including fallopian cancer or primary peritoneal cancer) harboring germline breast cancer susceptibility gene 1/gene 2 (BRCA1/2) mutation

# 3.2.2 Secondary Objectives

- To evaluate the efficacy of pamiparib as measured by progression free survival (PFS), duration of response (DOR) by both IRC and investigator review, and overall survival (OS) by investigator review
- To evaluate the efficacy of pamiparib as measured by the ORR by investigator review
- To evaluate the safety and tolerability of pamiparib
- To evaluate the efficacy of pamiparib as measured by disease control rate (DCR), best overall response (BOR) and clinical benefit rate (CBR) by both IRC and investigator review
- To evaluate the carcinoma antigen-125 (CA-125) response rate per Gynecological Cancer Intergroup (GCIG) for CA-125 changes
- To further characterize the PK of pamiparib

# 3.2.3 Exploratory Objectives

Version 1.1: 02/28/2020 Page 8 of 28

#### 4 STUDY ENDPOINTS

#### 4.1 Phase 1 Portion

BeiGene, Ltd.

# 4.1.1 Primary Endpoint

 Incidence of adverse events, overall and by severity, and incidence of SAEs according to National Cancer Institute Common Toxicity Criteria for Adverse Events, version 4.03 (NCI-CTCAE); laboratory abnormalities; changes in laboratory assessments, ECGs, and assessment of physical examinations.

#### 4.1.2 Secondary Endpoints

- PK parameters of pamiparib and possible its major metabolite(s): area under the plasma concentration-time curve (AUC), maximum observed plasma concentration (Cmax), and time to reach Cmax (Tmax); elimination half-life (t1/2), apparent clearance (CL/F), and apparent volume of distribution during terminal phase (Vz/F) and other applicable parameters.
- Efficacy assessment by the investigator based on the RECIST, v1.1:
  - ORR is defined as the proportion of patients who had confirmed CR or PR
  - DOR is defined as the time from the first determination of a confirmed overall response until the first documentation of progression or death, whichever comes first
  - DCR is defined as a BOR of CR, PR and stable disease (SD)
  - CBR is defined as a BOR of CR, PR and SD lasting ≥24 weeks
  - PFS is defined as the time from first dose of study medication to the first documented disease progression or death due to any cause, whichever occurs first

#### 4.1.3 Exploratory Endpoint

#### 4.2 Phase 2 Portion

# 4.2.1 Primary Endpoint

ORR as defined above in advanced HGOC patients by IRC

# 4.2.2 Secondary Endpoints

- DOR is defined as the time from the first determination of a confirmed overall response until
  the first documentation of progression or death, whichever comes first
- PFS is defined as the time from first dose of study medication to the first documented disease progression or death due to any cause, whichever occurs first
- OS is defined as the time from the first dose of study medication to the date of death due to any cause

Version 1.1: 02/28/2020 Page 9 of 28

- ORR as defined above in advanced HGOC patients by investigator review
- CA-125 response rate per GCIG criteria for CA-125 changes
- Incidence of AEs, overall and by severity, and incidence of SAEs; laboratory abnormalities; changes in laboratory assessments, ECGs, and assessment of physical examinations such as vital signs
- For patients participating intensive PK sample collection: AUC,  $C_{max}$ , and  $T_{max}$ ;  $t_{1/2}$ , CL/F,  $V_z/F$
- DCR and CBR as defined above

# 4.2.3 Exploratory Endpoints

5 SAMPLE SIZE CONSIDERATIONS

Approximately 14-18 evaluable patients will be enrolled in Phase 1 portion of the trial. In the Phase 2 portion of the trial, approximately 100 evaluable patients will be enrolled.

In recurrent HGOC patients, it is assumed that ORR is 52% with pamiparib in previously treated platinum-sensitive patients with BRCA mutation. A total of 80 evaluable patients will give 98% power to demonstrate a statistical difference versus a historical response rate of 30% using a binomial exact test at an alpha of 0.025. The 2-sided exact 95% CI is (40.5%, 63.3%) when the observed ORR is 52%. Approximately 20 patients will be enrolled to the platinum-resistant HGOC patients.

Hence, approximately 118 patients will be enrolled to obtain 14-18 evaluable patients in Phase 1 and 100 evaluable patients in Phase 2.

#### **6 STATISTICAL METHODS**

#### 6.1 ANALYSIS SETS

The Safety Analysis Set includes all patients who received at least one dose of pamiparib.

The Efficacy Evaluable Analysis Set includes all patients in the safety analysis set who had measurable disease at baseline per RECIST, v1.1 (based on investigator assessment for phase 1 and IRC assessment for phase 2) and had at least one post baseline tumor assessment unless discontinued treatment due to clinical progression or death prior to tumor assessment.

The DLT Analysis Set includes all patients who received at least 75% of pamiparib or who experienced a DLT event during the DLT observation period (Cycle 1).

The PK Analysis Set includes all patients for whom valid pamiparib PK parameters can be estimated.

Version 1.1: 02/28/2020 Page 10 of 28

The CA-125 Evaluable Analysis Set is defined as the subset of patients in the Safety Analysis Set with baseline CA-125  $\geq$  2 x ULN. This will be the primary analysis set for the analysis of CA-125 response rate.

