The date when the CA-125 level is first reduced by 50% is the date of the CA-125 response. To calculate response, an intent-to-treat analysis should be used that includes all patients with an initial CA-125 level of at least twice the upper limit of the reference range as eligible and evaluable. In addition, as a separate analysis, those patients who have a CA-125 response and whose CA-125 level falls to within the reference range can be classified as CA-125 complete responder see Table 5 for Phase 1, and Table 7 for Phase 2 where CA-125 is stated as normalized or normal, means within the reference range. Patients who have a fall of CA-125 to within the reference range but whose initial CA-125 was less than twice the upper limit of the reference range cannot therefore be classified as a CA-125 complete responder.

Table 11. CA-125 response measurement

CA-125 level	CA-125 measurement
Baseline CA-125 more than twice upper limit of normal, later reduced by	Complete response (CR)
50% to normal and maintaining for at least 28 days	
Baseline CA-125 more than twice upper limit of normal, later reduced by	Partial response (PR)
50% but not to normal	
CA-125 change out of range of PR and PD	Non-PR, non-PD
CA-125 increased at baseline returning to normal after treatment, later	Progressive disease (date of first
twice or higher upper limit of normal (two consecutive measurement at	evaluation of progression)
interval of at least one week)	
CA-125 increased at baseline not returning to normal after treatment,	Progressive disease (date of first
later twice or higher the lowest value (two consecutive measurement at	evaluation of progression)
interval of at least one week)	
CA-125 within reference range at baseline, later twice or higher upper	Progressive disease (date of first
limit of normal (two consecutive measurement at interval of at least one	evaluation of progression)
week)	

Reporting of response according to GCIG criteria that integrate CA-125 response with RECIST1.1 is shown in Table 12 and Table 13.

CA-125	Nontarget Lesions*	New Lesions	Overall Serological Response	Best Response for This Category Also Requires
Response and Normalized	CR	No	CR	Confirmed and maintained for at least 28 days
Response	Non-PD	No	PR	
Normalized but no response	Non-CR/Non- PD	No	SD	
Non-PR/non-PD	Non-PD	No	SD	
PD	Any	Yes or No	PD	
Any	PD†	Yes or No	PD	
Any	Any	Yes	PD	

Table 12.	Evaluation of best overall response in patients without initial measurable disease

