#### 6.4 EFFICACY ANALYSIS

A summary table for all the efficacy endpoints could be referred to in Table 1. Detailed information for each endpoint for each phase is elaborated in the following subsections.

**Version 1.1**: 02/28/2020 Page 13 of 28

(Statistical Analysis Plan)

Table 1. Summary table of efficacy endpoints and their corresponding analysis sets

	Phase 1			Phase 2			Phase 2		
Phase (Source)	(Investigator Review)		(Independent Review Committee)			(Investigator Review)			
Analysis Set 	A	В	С	A	В	С	A	В	С
ORR	Y	Y	-	Y	Y	-	Y	Y	-
DOR	$Y^2$	-	-	$Y^2$	-	-	$Y^2$	-	-
PFS	-	Y	-	-	Y	-	-	Y	-
OS	-	-	-	-	-	-	-	Y	-
DCR	Y	Y	-	Y	Y	-	Y	Y	-
CBR	Y	Y	-	Y	Y	-	Y	Y	-
CA-125 response rate	-	Y 	Y 	-	-	-	-	$Y^3$	Y 

Note: 1: A: Efficacy evaluable analysis set, B: Safety analysis set, C: CA-125 evaluable analysis set, Y: Yes. 2: only for responders. 3: only for HGOC patients.

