# 6.4.1 Primary Efficacy (Phase 2)

Hypothesis testing of ORR will only be performed in the patients with high grade platinum-sensitive ovarian cancer (PSOC). The primary analysis will be carried out using IRC data in efficacy evaluable analysis set. Efficacy endpoints based on investigator assessed tumor response will be presented as the sensitivity analysis. ORR of pamiparib per IRC is assumed as 52% in patients with recurrent PSOC. The historical rate in a similar population is estimated as 30%. The null and alternative hypotheses are set as follows:

H0: ORR=30% Ha: ORR >30%

A binomial exact test will be performed for hypothesis testing in recurrent PSOC efficacy evaluable analysis set. If the obtained one-sided p-value is  $\leq 0.025$ , it will be concluded that pamiparib monotherapy statistically significantly increases ORR compared with historical control. A two-sided binomial exact 95% CI of ORR will be constructed to assess the precision of the rate estimate.

The primary efficacy analysis will be conducted when mature response rate data have been observed, estimated as no more than 12 months after the last patient received the first dose of study drug.

Version 1.1: 02/28/2020 Page 14 of 28

ORR in evaluable recurrent high grade platinum-resistant ovarian cancer (PROC) will be summarized descriptively.

Sensitivity analysis of ORR will be carried out in the safety analysis set. Patients without postbaseline tumor assessment will be considered as non-responders in the safety analysis set and will be classified in category "not evaluated/not evaluable".

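### The only hypothesis test leaves out treated platinum-sensitive patients who were never scanned after baseline, which can only raise the response rate

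*SAP*

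**What the plan says.** SAP 6.4.1 confines hypothesis testing to PSOC patients and names the set: "The primary analysis will be carried out using IRC data in efficacy evaluable analysis set". Success is a one-sided exact binomial p-value of at most 0.025 against a null ORR of 30%. The null value is introduced only by the statement "The historical rate in a similar population is estimated as 30" (per cent). Protocol 10.3.1 gives the same rule.

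SAP 6.1 sets two conditions for a treated patient to be evaluable. The first is measurable disease at baseline, "based on investigator assessment for phase 1 and IRC assessment for phase 2". The second is that the patient "had at least one post baseline tumor assessment unless discontinued treatment due to clinical progression or death prior to tumor assessment". Protocol 10.2.1 has the same second condition.

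ORR counts confirmed CR or PR only (SAP 4.1.2, carried into 4.2.1). SAP 6.4.1 also plans a sensitivity ORR in the safety analysis set, where "Patients without postbaseline tumor assessment will be considered as non-responders in the safety analysis set". SAP Table 1 ("Summary table of efficacy endpoints and their corresponding analysis sets") lists ORR in both sets.

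The CA-125 response rate is handled differently. "The CA-125 Evaluable Analysis Set is defined as the subset of patients in the Safety Analysis Set" who meet a baseline CA-125 threshold, with no requirement for a later sample. Protocol Appendix 7 states: "To calculate response, an intent-to-treat analysis should be used that includes all patients with an initial CA-125 level" at or above that threshold.

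**The concern.** A treated patient with no scan after baseline cannot have a confirmed CR or PR. Removing that patient shrinks the denominator and leaves the numerator alone, so ORR rises and the exact p-value falls. The effect never runs the other way. In a randomised comparison a similar loss in the control arm might partly offset it; against a fixed 30% nothing does.

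The gap is narrow. Patients who stop for clinical progression or die before a scan stay in the set. Patients who stop treatment without documented progression continue to be scanned (Protocol Table 7 footnote 13, 7.3.4, 7.5.2 and 7.6). What remains is mainly full withdrawal, loss to follow-up, new anticancer therapy or missed scans before any post-baseline assessment. The documents do not say how many such patients to expect. The enrolment target of about 118 is 18 + 100, with no allowance for non-evaluable patients.

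At stake is whether a result just past the boundary could owe its success to one or a few unscanned patients.

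**Working it through.** **Inputs.** From SAP section 5 and 6.4.1: 80 evaluable PSOC patients, null ORR 0.30, assumed ORR 0.52, exact binomial test, one-sided alpha 0.025, stated power 98%. The number of unscanned patients, d, is not in the documents, so it is varied.

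**Step 1: reproduce the plan.** Find the smallest r with P(X ≥ r | n = 80, p = 0.30) ≤ 0.025.
- r = 32 gives 0.0360; r = 33 gives 0.0211. The test therefore rejects at 33/80 (41.25%) or more.
- Power is P(X ≥ 33 | n = 80, p = 0.52) = 0.979, which agrees with the stated 98%.

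**Step 2: tipping points.** Add d unscanned patients as non-responders to 80 scanned patients. Find the smallest d with P(X ≥ r | n = 80 + d, p = 0.30) > 0.025.

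| Responders r | ORR among 80 | d that removes significance | Result |
|---|---|---|---|
| 33 | 41.25% | 1 | 33/81, p = 0.0256 |
| 34 | 42.5% | 4 | 34/84, p = 0.0263 |
| 35 | 43.75% | 7 | 35/87, p = 0.0269 |
| 36 | 45.0% | 10 | 36/90, p = 0.0274 |
| 42 | 52.5% | 27 | 42/107, p = 0.0257 |

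At 42/80 itself, p = 0.00002.

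**Step 3: how often the decision would differ.** With d = 4 the critical count rises from 33 to 35, so the two sets disagree when X is 33 or 34. P(X = 33 or 34 | n = 80, p) is 0.035 at p = 0.52, 0.153 at 0.45 and 0.169 at 0.40. The last two rates are below the design assumption.

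**Step 4: effect on the estimate.** The shift in ORR is not confined to the boundary. With 42 responders, 42/80 = 52.5% (exact 95% CI 41.0% to 63.8%) becomes 42/84 = 50.0% (38.9% to 61.1%) with 4 unscanned patients.

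**Step 5: type I error, under a condition.** For the hypothesis as written, in the evaluable set, the attained level is 0.0211. It can exceed 0.025 only if the 30% is a rate among treated patients, which the documents do not say.
- *80 evaluable plus d dropped.* The scanned rate under the null is 0.30 × (80 + d)/80. P(X ≥ 33 | n = 80) at that rate is 0.0253 for d = 1 (rate 0.30375), 0.030 for d = 2 (0.3075) and 0.042 for d = 4 (0.315). The error reaches 0.025 at a rate of 0.3035, that is, dropout of 1 − 0.30/0.3035 ≈ 1.2%.
- *N = 80 to 89 treated, each unscanned with probability f.* The number scanned is m ~ Binomial(N, 1 − f), X ~ Binomial(m, 0.30/(1 − f)), and the critical value is recomputed for each m. The error is 0.020–0.024 at f = 1%, 0.024–0.027 at 2% and 0.038–0.041 at 5%. It crosses 0.025 at f between 1.4% (N = 80) and 2.1% (N = 85).

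**Step 6: the safety set is a different comparison.** It drops the scan condition but also restores patients without IRC-measurable disease, who are not certain non-responders. For example, 33/80 plus one unscanned patient plus one responder without IRC-measurable disease is 34/82, p = 0.0179. Neither planned set isolates the scan condition.

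**The case against.** The strongest reply is that nothing here is invalid. The hypothesis, the sample size and the test are all stated for evaluable patients, consistently in protocol and SAP, and the test holds its level. Preferring an all-treated population is a choice of estimand. That is correct, and this point does not claim an error against the hypothesis as written.

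A second reply is that the plan already covers this. The safety-set ORR counts unscanned patients as non-responders, so any reader will see the effect. That stands in part and limits the seriousness. But the success rule does not use that analysis, the plan does not say how a disagreement would be read, and the safety set changes a second condition at the same time (Step 6).

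Third, few patients are likely to be affected, and at 52% the decision would rarely change. Both are true; the documents give no count, and it could be zero.

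Fourth, the type I error figures rest on an unknown denominator for the 30% and on assumed dropout. This is also correct. They are conditional and should not carry the argument. The CA-125 comparison is only supportive: Appendix 7 reproduces guideline text for a secondary marker endpoint and does not govern RECIST response.

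Finally, a lighter remedy would be to state in advance how a disagreement between the two sets will be interpreted. That would help, but the success rule would still rest on a set that leaves out certain non-responders.

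**Conclusion.** The concern holds. The one confirmatory decision rests on a set that omits some certain non-responders, and the omission works in one direction only. The decision is fragile only close to the critical value: one unscanned patient reverses 33/80, and four reverse 34/80. At the design effect it is robust, since 42/80 would need 27. These tipping points assume 80 scanned PSOC patients and compare sets that differ only in unscanned patients.

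The type I error exceeds 0.025 only if the 30% is a treated-patient rate, and then from about 1.2% to 2.1% dropout depending on the model. This should be fixed because the remedy is cheap, applies the non-responder rule the SAP already uses for the safety set, and closes a foreseeable challenge to the primary result.

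**What to change.** Before database lock:

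- Run the exact test in all treated PSOC patients with measurable baseline disease by IRC. Remove the post-baseline-scan condition for this test and count patients with no post-baseline assessment as non-responders.
- Keep the current evaluable set and the planned safety-set ORR as supportive analyses.
- Report the number of PSOC patients with no post-baseline assessment, with reasons.
- Edit SAP 6.1 and 6.4.1. Either amend Protocol 10.2.1 and 10.3.1 or record the change in SAP section 8, which at present lists none.

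No new data are needed. ORR in the new set is the same as in the current evaluable set or slightly lower. If 80 patients are scanned and respond at 52%, applying the critical count for the enlarged denominator (34 for n = 82, 35 for n = 84, 36 for n = 88) to Binomial(80, 0.52) gives power of 96.5% with 2 unscanned, 94.4% with 4 and 91.4% with 8, against 97.9% with none.
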